Nirogacestat had a manageable safety profile and was tolerated by the majority of patients. The frequency of patients that experienced at least 1 TEAE was similar between treatment arms (69 patients [100%] in the nirogacestat arm and 69 patients [96%] in the placebo arm). In the nirogacestat arm, the majority (95%) of TEAEs were Grade 1 or Grade 2. The most frequently reported (> 30% of patients) TEAEs in the nirogacestat arm were diarrhea, nausea, fatigue, hypophosphatemia, and rash maculo-papular. Events of ovarian dysfunction (as defined by the preferred terms of menopause, premature menopause, ovarian failure, and amenorrhea) were also commonly reported in women of childbearing potential (27/36 [75%]) receiving nirogacestat. More Grade \geq 3 events occurred in the nirogacestat arm compared to placebo; diarrhea had the greatest imbalance in incidence with 16% in the nirogacestat arm vs 1% in placebo. A total of 21 patients (15%) experienced an SAE, including 14 patients (20%) in the nirogacestat arm and 7 patients (10%) in the placebo arm. The only preferred term (PT) reported as serious by > 1 patient in the nirogacestat arm was premature menopause (3 patients). One death occurred; this event of sepsis was in the placebo arm and was considered by the investigator to be unrelated to study treatment. Sixteen (23%) patients receiving nirogacestat had TEAEs leading to study treatment discontinuation; 2 of these 16 patients also had clinical progression as the primary reason for treatment discontinuation and the reported TEAEs were manifestations of the progression. Excluding the discontinuations due to clinical progression, 14 (20%) patients discontinued due to TEAEs. The TEAEs leading to discontinuation of study treatment of > 1 patient in the nirogacestat arm were diarrhea, premature menopause, ALT increased, and AST increased. The overall benefit / risk balance for nirogacestat treatment of adult patients with DTs was favorable, with a substantial reduction in the risk of disease progression, an increase in the objective response rate, and significant and clinically meaningful improvements in pain, DT-specific symptom burden and their impact on patient lives, physical functioning, role functioning, and health-related quality of life, balanced with a manageable safety profile.

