3.7. Subject Study Completion or Termination

3.7.1. Definition of Off-study by Subject Completion

Subjects are considered to have completed the study when any of the following criteria are met:

- Protocol-specified treatment and per protocol follow-up have been completed.
- Females reporting ovarian dysfunction including ovarian failure, menopause, premature menopause and/or amenorrhea have been followed until event resolution or for at least 90 days after discontinuing study treatment.
- Disease progression and per protocol follow-up have been completed.
- Death

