3.7.2. Investigator-initiated Discontinuation of Study Treatment

The investigator may require a study subject to discontinue study treatment in the event of one of the following:

- The study subject has disease progression.
- Noncompliance
- The study subject needs treatment not allowed in the study.
- Pregnancy

- The study subject develops an AE that cannot be tolerated or that cannot be controlled with other medication.
- The investigator feels that it is in subject's best interest to stop treatment.
- The study subject is unable to meet study requirements.
- New information about the treatment of desmoid tumor becomes available.

If study therapy is stopped but the study subject allows the physician to submit follow up information, subject will continue to be followed clinically according to the study schedule.

If a subject must be removed from the study, the reason for the study removal and the date the subject was removed will be documented in the subject documentation/Case Report Form (CRF).

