3.7.3. Subject-initiated Discontinuation of Study Treatment

Even after a subject agrees to take part in the study, they may stop therapy or withdraw from the study at any time. If the study participant stops treatment but still allows the study physician to submit follow up information (progression and survival information), the subject will continue to be followed clinically according to standard of care. Alternatively, the subject may withdraw consent and choose to have no further interaction regarding the study.

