6. STUDY PROCEDURES AND ASSESSMENTS

6.1. Schedule of Events

Cycle Length: 28 days

Labs, Tests, Procedures, Drug Administration ^a	Screening ^b	Cycles 1–6 ^c	Cycles 7 – 26 ^c	End of Treatment (EOT) ^d
Nirogacestat ^e		X	X	
Cryoablation ^f		X		
Informed consent	X			
Demographics	X			
Medical history	X			
Concomitant medications ^g	X	X	X	X
Physical exam	X	X	X	X
Vital signs	X	X	X	X
Height	X			
Weight	X	X	X	X
Performance status	X	X	X	X
EQ-5D-3L questionnaire ^h	X	X	X	X
CBC w/differential ⁱ	X	X	X	X
Serum chemistry, magnesium, phosphorus ^j	X	X	X	X
Coagulation (PT, PTT)	X			
β-HCG ^k	X			
Urine pregnancy test ^l		X	X	X
ECG ^m	X			
Adverse event evaluation ⁿ	X	X	X	X
Tumor measurements ^o	X	X	Tumor measurements at Screening, then every 3 cycles (every 12 weeks ± 14 days) until End of Treatment (EOT) Visit. Subjects who come off treatment for reasons other than progressive disease may have imaging for EOT visit at the discretion of the provider.	
Radiologic evaluation (MRI) ^o	X	X	Radiologic evaluation at Screening, then every 3 cycles (every 12 weeks ± 14 days) until EOT Visit. Subjects who come off treatment for reasons other than progressive disease may have imaging for EOT visit at the discretion of provider. Documentation (radiologic or clinical) must be provided for subjects removed from study for PD.	
Archival histology report ^o	X			

Correlative studies ^p	X	X		

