An End of Treatment visit will be done within 30 days of last treatment \pm 7 days. Subjects will be followed for safety for 30 days from time of last treatment, except if being monitored for related adverse event.

The following procedures/assessments may be performed at the EOT visit:

- Subjects may be seen in person, by video visit, or may be contacted by phone. If in-person visit, then physical exam, vital signs, weight and EQ-5D-3L questionnaire will be done.
- If a video visit or phone visit is done, then EQ-5D-3L questionnaire will be sent to the subject via secure Email or MyHealth Epic message for the subject to complete and return via secure Email or MyHealth Epic message.
- Vital signs and weight will be done if subject has in-person visit.
- EQ-5D-3L Questionnaire: See above.
- Adverse event assessment
- Review of concomitant medications
- Performance status assessment
- Routine labs
- Urine pregnancy test
- Radiographic evaluation and tumor measurement: Subjects who come off treatment for reasons other than progressive disease may have imaging for EOT visit at the discretion of the provider.
- Other assessments to be done at the discretion of the treating investigator.

Subjects that personally withdraw from treatment will be requested to have a 30-day End of Treatment visit or otherwise receive a follow-up contact, unless specifically countermanded by the subject.

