10.2. Study Endpoints and Analyses

10.2.1. Primary Endpoint and Analysis

10.2.1.1. Primary Endpoint

The clinical benefit rate (CBR) is defined as the number and proportion of participants who are assessed with either a complete response (CR), a partial response (PR), or stable disease (SD) prior to 1 year after treatment start and show no evidence of loss of response nor progression

within that year. Response and progression will be assessed according to the Revised Response Evaluation Criteria in Solid Tumors (RECIST) v1.1.

10.2.1.2. **Primary Analysis Plan**

The primary analysis will be the calculation of the clinical benefit rate, (CBR), defined as the percentage of subjects in the analysis population who achieve a complete response (CR), partial response (PR), or stable disease (SD) as measured at 12 months \pm 1 month (approximately 1 year) from the start of treatment. CR, PR, and SD are as defined by RECIST v1.1. (See Appendix C RECIST v1.1). The CBR and the two-sided 95% Clopper-Pearson (exact) confidence interval will be calculated.

The analysis population will include all subjects who started nirogacestat and underwent cryoablation. Subjects who withdraw from the study prior to start of treatment or before receiving cryoablation and completing 1 year of treatment will be replaced.

10.2.1.3. **Relevant Subset for Primary Objective and Endpoint**

Evaluable subjects are those subjects who have received cryoablation therapy and completed 1 year of treatment.

10.2.1.4. **Primary Objective and Endpoint Assessment Methods**

CBR will be evaluated on the basis of clinical response as measured using imaging by MRI scan and evaluated by RECIST v1.1 (Appendix C). Determination of response will be made by the treating investigator.

10.2.1.5. **Measurement Time Points for Primary Objective / Outcome**

Imaging will be performed at screening, then every 3 cycles (ie, every 12 weeks \pm 14 days) until End of Treatment. MRI scan will be used at screening and at subsequent time points.

10.2.2. **Secondary Endpoints and Analysis**

10.2.2.1. **Clinical Benefit Rate (CBR) assessed by modified RECIST**

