For tumors with MRI enhancement, CBR will be evaluated on the basis of clinical response as measured using imaging by MRI scan and evaluated by modified RECIST (Appendix D). Determination of response will be made by the treating investigator. Imaging will be performed at screening, then every 3 cycles (ie, every 12 weeks \pm 14 days) until End of Treatment. MRI scan will be used at screening and at subsequent time points.

10.2.2.2. **Median Progression-free Survival (PFS)**

Median progression free survival (PFS) will be measured using imaging by MRI scan and evaluated by RECIST v1.1, mRECIST, and volumetrically (change in tumor volume as assessed by MRI volumetric).

Progression-free survival is defined as the time from start of treatment to date of progression or death due to any cause. If a subject is not known to have progressed or died, then PFS will be censored at the latest date the subject was known to be alive or progression-free (on or before the cut-off date). The PFS distribution will be estimated using the Kaplan-Meier method, and

the Kaplan-Meier curves, medians and 95% confidence intervals of the medians will be presented.

10.2.2.3. **Objective Response Rate (ORR) at 1 year**

For the objective response rate (ORR) at 1 year, the percentage of subjects who start study treatment and achieve an objective response (CR or PR) will be calculated. ORR will be measured using imaging by MRI scan and evaluated both RECIST v1.1, mRECIST, and MRI volumetric.

The ORR will be calculated as the proportion of subjects with objective response. The ORR and the two-sided 95% Clopper-Pearson (exact) confidence interval will be calculated.

10.2.2.4. **Time to Response (TTR)**

Time to response is defined as the time from the start of treatment with nirogacestat to the first objective tumor response (CR or PR), and will be measured using imaging by MRI scan and evaluated by RECIST v1.1, mRECIST, and volumetrically.

The TTR distribution will be estimated using the Kaplan-Meier method, and the Kaplan-Meier curves, medians and 95% confidence intervals of the medians will be presented.

10.2.2.5. **Duration of Response (DoR)**

Duration of response (DoR) is defined as the time from the date of documented disease response (CR or PR) to the date of the first documented progression, and will be determined using imaging by MRI scan and evaluated by RECIST v1.1, mRECIST, and volumetrically.

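### PFS is read from MRI but censored at the last date alive or progression-free, so contact without a scan can count as progression-free time; the effect is small, upward only, and confined to secondary PFS

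*Protocol*

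**What the plan says.** Section 10.2.2.2 states that PFS is determined from MRI, read by RECIST v1.1, mRECIST and volume. The event is progression or death from any cause, and the curve and median are Kaplan-Meier estimates. For a subject without an event, "PFS will be censored at the latest date the subject was known to be alive or progression-free", on or before the cut-off date.

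The passages that govern scans and contact after stopping are these:

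- Imaging is every 12 weeks ± 14 days "until End of Treatment. MRI scan will be used at screening and at subsequent time points" (Section 10.2.1.5). The Schedule of Events (Section 6.1) has scans "until EOT Visit. Subjects who come off treatment for reasons other than progressive disease may have imaging for EOT visit", at the provider's discretion.
- The EOT visit falls 30 ± 7 days after last treatment. "Subjects may be seen in person, by video visit, or may be contacted by phone" (Section 6.2.2).
- Women with ovarian dysfunction complete the study once they "have been followed until event resolution or for at least 90 days after discontinuing study treatment" (Section 3.7.1).
- A subject who chooses to stop but allows follow-up information to be submitted is covered by Section 3.7.3: "progression and survival information), the subject will continue to be followed clinically according to standard of care". It sets no scan schedule and no end date.
- For a subject stopped by the investigator, the "subject will continue to be followed clinically according to the study schedule" (Section 3.7.2). That schedule lists no scan after EOT.

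**The concern.** Radiographic progression can be seen only on a scan. If a phone call 30 days after the last dose moves the censoring date past the next planned scan, the subject sits in the Kaplan-Meier risk set at a scan that was never done and cannot contribute a radiographic event there. The denominator grows and the numerator does not.

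Subjects who stop without progression are to be expected. In the phase 3 trial of nirogacestat, "Excluding the discontinuations due to clinical progression, 14 (20%) patients discontinued due to TEAEs" (Section 1.2.4). This trial has one arm, and the synopsis lists PFS among its descriptive statistics and plans a comparison with historical controls. No concurrent arm would share an upward error in PFS. The protocol fixes the censoring rule itself, so this is not a detail left to a later plan.

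**Working it through.** **Figure to reproduce.** None. The protocol states no assumed PFS, event count or PFS power.

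**Direction.** Kaplan-Meier PFS is S(t) = ∏(1 − dᵢ/nᵢ) over event times. With event dates fixed, moving a censoring date later leaves every dᵢ unchanged and can only keep or raise nᵢ. So S(t) and the median cannot fall. As an illustration, suppose 20 subjects are still in contact at a scan date, 2 of them stopped earlier and were not scanned, and 2 progressions are seen:

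- last-scan rule: 1 − 2/18 = 0.889
- rule as written: 1 − 2/20 = 0.900, which is 1.1 points higher

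**How often contact passes a missed scan.** Scans are 84 days apart. With 30-day contact the share of progression-free stoppers carried past a missed scan is about 30/84 = 0.36 (simulated 0.36 to 0.38). With 90-day contact it is all of them, since 90 > 84.

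**Inputs to the size calculation.**

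- Scans every 84 days to day 672; contact 30 days after stopping (EOT visit) or 90 days (ovarian-dysfunction follow-up): from the protocol.
- True 12-month PFS of 0.8 and 0.5: the alternative and null CBR of Section 10.4.2, used as stand-ins (assumption).
- 20% stopping without progression: anchored on 14/69 = 0.203 in the phase 3 trial, whose follow-up length the protocol does not give. Stopping is therefore placed either wholly in year 1 or across 24 months (assumption).
- Exponential PFS, no deaths, and no scan at or after stopping (assumptions).

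The 12-month value is read at the day-336 scan. This gives 0.8^(336/365) ≈ 0.814 and 0.5^(336/365) ≈ 0.528 under correct censoring. The scan-grid offset is the same under both rules and cancels in the difference.

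**Large-sample result, 20% stopping in year 1.**

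| True PFS | Contact | Last-scan rule | Rule as written | Difference (points) |
|---|---|---|---|---|
| 0.8 | 30 d | 0.8145 | 0.8179 | +0.3 |
| 0.8 | 90 d | 0.8154 | 0.8243 | +0.9 |
| 0.5 | 30 d | 0.5278 | 0.5351 | +0.7 |
| 0.5 | 90 d | 0.5273 | 0.5467 | +1.9 (a rerun gave almost +2.0) |

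If the same 20% is spread over 24 months, the differences roughly halve: +0.17 and +0.35 points with 30-day contact, +0.45 and +0.97 with 90-day contact (80% and 50% cases). The overall ranges are therefore about 0.2 to 0.7 and 0.5 to 2.0 points.

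**Median.** In large samples it is the same under both rules: 420 days in the 50% case, and not reached by day 672 in the 80% case. At N=20 the reported median differs between the rules in about 0 to 1% of trials (80% case) and 3 to 13% (50% case), always upward.

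**Sampling error for scale.** The SD of the 12-month estimate at N=20 is about 9.5 points (80% case) and 12 points (50% case).

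**Longer unscanned contact.** Section 3.7.3 gives no length, so this is a scenario only. A separate simulation had 20% off treatment by one year. Contact of 26 weeks without a scan added 1.6 to 3.7 points at one year. Contact of 52 weeks added 2.2 to 5.3 points, and the typical median in the 50% case moved from 60 to 72 weeks.

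**The case against.** The strongest reply is that this hardly matters. The named statistic is the median, which usually does not move. The registry version in Section 2.3.2.2 is a count at one year, no decision rule uses PFS, and the bias is far below the sampling error. That is a fair account of the size. It does not defend the rule, because the error runs one way, appears on the Kaplan-Meier curves to be presented, and shifts some medians at N=20.

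A second reply is that the scenarios lean upward. EOT scans are discretionary, not absent: if half the stoppers are scanned, the 30-day, year-1 figures fall to about +0.18 and +0.38 points. Ovarian follow-up may also end at resolution, before 90 days. This stands, and the figures should be read as conditional.

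A reader might infer that progression cannot be detected at all after the last scan. The documents do not support that. Section 6.1 accepts clinical as well as radiologic documentation for removal for progression, and Section 3.7.3 collects progression information. Both soften the bias, although an alive-only contact does not.

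A reader might also infer that the EOT-imaging passages contradict one another. Some list EOT imaging without qualification, but the exception for subjects who stop without progression is stated in Sections 6.1 and 6.2.2, so they read as a rule with an exception. Nor does this point bear on the volumetric thresholds of Appendix E, which have nothing to do with censoring.

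**Conclusion.** The censoring rule is wrong as written for an endpoint determined by imaging, and no other passage restricts it to the last scan. With event dates fixed it can only keep or raise PFS under all three criteria. At the planned contact lengths the effect is small: about 0.2 to 0.7 points at 12 months with 30-day contact and 0.5 to 2.0 points with 90-day contact. These figures assume 20% stopping without progression, no EOT scan, exponential PFS, and true 12-month PFS of 80% to 50%. Longer unscanned follow-up would enlarge the bias; EOT scans or reported progression would reduce it.

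It would be going too far to say that median PFS is materially inflated, or that the trial's conclusion is at risk. The median is unchanged in large samples and in most trials of 20, and the primary CBR does not use this rule.

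**What to change.** In Section 10.2.2.2, replace the censoring rule with: *PFS will be censored at the date of the last evaluable tumour assessment showing no progression by the criterion in question (day 1 if none).* Add that evaluable standard-of-care scans reported under Section 3.7.3 count as assessments. Deaths remain events, as now.

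The cost is one or two sentences and no added scans. The only downside is a slightly lower reported PFS, by roughly the amounts above.

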10.3. Interim Analysis

No interim analysis is planned.

10.4. Sample Size

10.4.1. Accrual estimates

Stanford sees approximately 30 to 40 adult subjects annually in the Sarcoma Clinic with desmoid tumor. This study will enroll up to 23 subjects, in order to achieve 20 evaluable subjects. It is estimated that approximately 23 subjects can be enrolled within 24 months at Stanford University.

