Statistical Considerations	
Descriptive statistics (response rate, time to response, progression-free survival). Comparison to historical controls of nirogacestat alone and Stanford-treated cryoablation patients.
 
The primary outcome is clinical benefit rate (CR + PR + SD) at 1 year. We plan to enroll a total of 20 subjects. Assuming a null CBR of ≤ 0.5 versus an alternate CBR of 0.8, we have a maximum statistical power of 100.0% to detect a difference of 0.3 using a one-sided exact test with a type 1 error of 0.05.

Study Duration	
Duration of treatment for a subject via this study protocol is up to 24 months (26 cycles of treatment). This study will be complete when the last study data, including follow-up, has been collected, and analysis is complete. The duration of enrollment for this study will be approximately 25 months (including the initial 28-day screening period). Based on the determination of clinical benefit after 12 months' treatment, and 3 months for analysis of the primary endpoint, preliminary results for the primary endpoint are expected to be available approximately 40 months from the start of enrollment. Based on 25 months to completely enroll, and overall individual treatment period of approximately 24 months, the overall period until treatment is complete will be about 49 months from the start of enrollment. The complete final analysis (including primary and secondary analyses and safety assessments) and termination of all study activities is expected to be at about 53 months.
 
Key milestones are as follows.
 
• The per-subject screening period is approximately 28 days.• The duration of enrollment (minus the screening period) is approximately 24 months.• The per-subject primary endpoint (clinical benefit) is assessed after 12 months' treatment.• The per-subject duration of treatment is approximately 24 months (26 cycles of treatment).• Final subject visit is about 30 days after last treatment.• Nominal duration of subject participation is up to about 26 months.• Final study analysis is expected to take about 3 months.
Subject Duration	Approximately 26 months (28-day screening period, approximately 24 months of treatment, and End of Treatment visit about 30 days after last study treatment).

PROTOCOL SCHEMA

Subject Consent

Screening (Day 1 to Day 28):

(Collect archival histology report, EQ-5D-3L questionnaire, ECG, serum pregnancy test, routine labs & scans).

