10.4.2. Sample Size Justification

We calculated power using a one-sample proportion test to determine if a population proportion is significantly different from hypothesized value. We define our hypotheses as:

Null hypothesis (H_0) that the proportion is $P_0 = 0.5$

Alternative hypothesis (H_1) that the proportion is $P_1 = 0.8$.

To test our hypothesis of clinical improvement:

$$H_0: P \leq P_0 \text{ vs } H_1: P = P_1 > P_0$$

Our sample size of 20 achieves 100.0% power to detect a difference ($P_1 - P_0$) of 0.3 using a one-sided exact test at an alpha level of 0.05. The results assume that population proportion under the null hypothesis is 0.5. Power was also computed using the normal approximation method.

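### A cap of 23 enrolled is unlikely to yield 20 evaluable subjects if evaluable means completing 1 year of treatment, as Section 10.2.1.3 defines it; it probably suffices for the conflicting population in Section 10.2.1.2

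*Protocol*

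**What the plan says.** Section 10.4.1 sets the accrual: "This study will enroll up to 23 subjects, in order to achieve 20 evaluable subjects". The synopsis and Section 2.1.3 repeat this. The synopsis paragraph on statistics differs: "We plan to enroll a total of 20 subjects". No assumed loss rate is given.

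Section 10.2.1.3 defines the term: "Evaluable subjects are those subjects who have received cryoablation therapy and completed 1 year of treatment". Section 10.2.1.2 gives another set for the primary analysis: "The analysis population will include all subjects who started nirogacestat and underwent cryoablation". It adds that subjects who withdraw before starting treatment, or "before receiving cryoablation and completing 1 year of treatment will be replaced".

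Sections 3.5 and 5.4 end treatment at progression or intolerance, among other reasons. Section 10.4.2 takes a null CBR of 0.5 and an alternative of 0.8, and says: "Our sample size of 20 achieves 100.0% power to detect a difference". Section 10.4.4 ties its decision count of 11 to a total of 20.

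**The concern.** The promise of 20 uses a defined term, and the definition removes anyone who does not finish a year of treatment. Progression ends treatment, and the trial's own alternative allows 20% of subjects to be without benefit at 1 year. That exceeds the 13% allowance before any adverse-event stop is counted.

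Two things are at stake. The decision count and power are stated only for 20, and the cap leaves just three replacements, so the trial may end with a size for which no rule is written. The definition also removes progressors from the CBR denominator. Those who remain are largely progression-free by construction, and a target of 0.8 against 0.5 then loses its meaning.

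**Working it through.** **Inputs.** Cap 23 and target 20 (10.4.1). CBR 0.8 and 0.5 (10.4.2). Phase 2 desmoid study: 1 of 17 permanently stopped for an adverse event (1.2.4). Phase 3: "Excluding the discontinuations due to clinical progression, 14 (20%) patients discontinued due to TEAEs", which is 14 of 69 on nirogacestat (1.2.4).

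**The plan's own figure.** No loss rate is stated, so 23 can only be solved backwards: 3/23 = 13.0%. With a 13% loss, 20/(1 − 0.13) = 22.99, which rounds up to 23. Even then, P(at least 20 of 23) is only 0.65.

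**Progression alone, under 10.2.1.3.** Assume that every subject without benefit progresses, stops treatment and is not evaluable. The evaluable count is then Binomial(23, CBR).

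- CBR 0.8: expected 23 × 0.8 = 18.4. P(20) + P(21) + P(22) + P(23) = 0.163 + 0.093 + 0.034 + 0.006 = 0.30. Enrolment for 20 on average: 20/0.8 = 25.
- CBR 0.5: expected 11.5. P(at least 20) = (1771 + 253 + 23 + 1)/2^23 = 2048/8,388,608 = 0.0002.

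**Adverse-event stops.** The last two rows multiply the retention rates, which assumes that the two causes are independent and do not overlap.

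| Loss counted | Proportion retained | Expected of 23 | P(at least 20) |
|---|---|---|---|
| Adverse events only, 1/17 | 0.941 | 21.6 | 0.96 |
| Adverse events only, 14/69 | 0.797 | 18.3 | 0.28 |
| Progression (CBR 0.8) and 1/17 | 0.753 | 17.3 | 0.14 |
| Progression (CBR 0.8) and 14/69 | 0.638 | 14.7 | 0.01 |

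**Under 10.2.1.2.** Only losses before cryoablation count, roughly the first 2.8 months (three 28-day cycles). The protocol gives no rate for this period. As an assumption, spread 14/69 at a constant hazard over a horizon of T months, with T from 12 to 30. The early loss is 1 − (55/69)^(2.8/T), which is 5.2% at T = 12 and 2.1% at T = 30. P(at least 20 of 23) is then 0.97 to above 0.99.

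**Exact test at n = 20, null 0.5, alternative 0.8.**

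| Successes needed | One-sided alpha | Power |
|---|---|---|
| 11 (Section 10.4.4) | 0.412 | 99.7% |
| 14 | 0.058 | 91.3% |
| 15 | 0.021 | 80.4% |

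The smallest count that keeps alpha at or below 0.05 is 15. The stated 100.0% matches only the count of 11, which does not hold the stated alpha.

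**The case against.** The strongest reply is that the primary analysis uses the 10.2.1.2 population, for which 23 is probably enough. That stands for 10.2.1.2. It does not rescue the sentence in 10.4.1, which promises evaluable subjects, a term that 10.2.1.3 defines otherwise.

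Second, progressors may never be replaced or dropped. The replacement rule speaks of withdrawal from the study. Section 3.7.1 treats progression with completed follow-up as study completion, and Section 3.7.2 keeps subjects in follow-up after an investigator stops therapy, if they allow it. A CBR of 0.8 also makes sense only with progressors in the denominator. All of this is fair and shows what was probably intended, but 10.2.1.3 as written excludes them.

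Third, 23 is a planning judgement with no stated loss rate, so no calculation is wrong. Agreed: the fault is a conflict between the target and its definition.

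Some stronger readings are tempting but unsupported.

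- A reader might take 20% as the 1-year adverse-event loss. Section 1.2.4 gives no horizon for that figure and refers to follow-up of 24 months. The phase 2 figure of 6% lies well under the 13% allowance, so adverse events alone do not settle the matter.
- A reader might compute power at a CBR of 0.8 for the reduced evaluable counts. That counts progressors twice, once as lost subjects and again as failures.
- A reader might add the 22% Grade 3-4 toxicity quoted for cryoablation (1.3.2). The protocol does not present it as a rate of stopping treatment.

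**Conclusion.** The point holds under Section 10.2.1.3. At the design alternative, 23 enrolled reach 20 evaluable with a probability of about 0.30 from progression alone, and lower once adverse-event stops are added. This rests on the subjects without benefit progressing and stopping within the year. The size of the adverse-event contribution is uncertain (6% to 20% in the protocol's own sources), and the combined figures also assume independence.

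The point does not hold under Section 10.2.1.2, where the cap is probably adequate. It would go too far to say that the trial cannot deliver 20 analysed subjects. The protocol gives two populations, and its stated size is likely to be met under only one of them.

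**What to change.** In Sections 10.2.1.3, 10.4.1 and 2.1.3 and in the synopsis:

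1. Define the design size as 20 subjects who have begun nirogacestat and had the cryoablation, which is the 10.2.1.2 population. Remove the 1-year requirement from the definition of evaluable.
2. Keep subjects who progress or stop before 1 year in the CBR denominator, counted as without clinical benefit unless a 1-year assessment shows it.
3. Limit replacement to subjects lost before cryoablation, so that the cap of 23 covers only those losses. Align the synopsis sentence that plans 20 enrolled.
4. In Sections 10.4.2 and 10.4.4 and the synopsis, state the exact rule for n = 20: at least 15 successes, one-sided alpha 0.021, power 80.4% at 0.8.

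Lowering the stated evaluable number to what 23 would yield under 10.2.1.3 is not a good alternative, because it would entrench a denominator that drops failures.

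The cost is wording only, with no extra subjects. The stated power falls from 100.0% to 80.4%, and the reported CBR may be lower because early stoppers stay in.
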